Methylprednisolone in adjunctive to endovascular treatment for patients with acute ischemic strokes with established large infarct: A multicenter, randomized, double-blind, placebo-controlled trial

(MIRACLE)

Study Protocol

Version number: V 2.0

NCT number: NCT06360458

Release date: July 23, 2024

Sponsor: The First Affiliated Hospital of Fujian

Medical University

Principal [name] M D, P h D

Confidentiality Statement

All information contained in this protocol is owned by the sponsor. Therefore, it is only provided for review by relevant medical institutions such as researchers, ethics committees, and regulatory authorities. Without written approval from the sponsoring unit, it is strictly prohibited to disclose any information to third parties unrelated to this study, except for necessary explanations when signing the informed consent form with patients who may participate in this study.

List of Abbreviations

Abbreviations	Annotation
AE	Adverse Event
aSICH	Asymptomatic Intracranial Hemorrhage
ASPECTS	Alberta Stroke Program Early CT Score
CRF	Case Report Form
CT	Computed Tomography
CTA	Computed Tomography Angiography
DSA	Digital Subtraction Angiography
DSMB	Data Safety Monitoring Board
EQ-5D	European Quality Five-Dimension
FAS	Full Analysis Set
GCP	Good Clinical Practice
ITT	Intention-to-Treat
MRA	Magnetic Resonance Angiography
MRI	Magnetic Resonance Imaging
mRS	modified Rankin Scale
NIHSS	National Institutes of Health Stroke Scale
PPS	Per-Protocol Set
QF	Query Form
SAE	Serious Adverse Event
SICH	Symptomatic Intracerebral Hemorrhage

Study Synopsis

Study Title	Methylprednisolone in adjunctive to endovascular treatment for patients with acute ischemic strokes with established large infarct: A multicenter, randomized, doubleblind, placebo-controlled trial (MIRACLE)		
Principal Investigators	[name] [name]		
Study Design	A multicentre, prospective, randomized, double-blind, placebo-controlled trial		
Efficacy Endpoints			
Primary Endpoint	Mortality at 90 ≠ days;		
Secondary Endpoints	1) mRS score improvement at 90 ≠ days (shift analysis); 2) Proportion of patients with mRS score 0 to 4 at 90 ≠ days (%); 3) Proportion of patients with mRS score 0 to 3 at 90 ≠ days (%); 4) Proportion of patients with mRS score 0 to 2 at 90 ≠ days (%); 5) Proportion of patients with mRS score 0 to 1 at 90 ≠ days (%); 6) mRS score improvement at 1 year (shift analysis); 7) Proportion of patients with mRS score 0 to 2 at 1 year (%); 8) Proportion of patients with mRS score 0 to 1 at 1 year (%); 9) mRS score improvement at 5 years (shift analysis); 10) Proportion of patients with mRS score 0 to 2 at 5 years (%); 11) Proportion of patients with mRS score 0 to 1 at 5 years (%); 12) NIHSS score at 5-7 days or at early discharge; 13) Health-related quality of life [European Quality of Life Five-Dimension visual-analogue scale (EQ-5D VAS)] at 90 ≠ days; 14) Proportion of patients with malignant cerebral edema within 48 hours after EVT (%) 15) Proportion of patients with secondary decompressive craniectomy(%) 16) EQ-5D VAS at 1 year;		
	17) EQ-5D VAS at 5 years.		
Safety Endpoints			
Primary Endpoints	Proportion of patients with symptomatic intracranial haemorrhage (SICH) within 48 hours after EVT		
Secondary Endpoints	Proportion of patients with asymptomatic intracranial haemorrhage (aSICH) within 48 hours after EVT;		
	 Incidence of any complications (including non-hemorrhagic serious adverse events such as gastrointestinal bleeding, urethral bleeding, oral or nasal mucosal bleeding, and subcutaneous hematoma, etc; or complications related to procedures and devices such as arterial rupture, arterial dissection, implantation failure, stent fracture, vascular puncture site complications, vasospasm, and device malposition, etc); Incidence of any adverse events (including cerebral hernia, pneumonia, 		
	respiratory failure, circulatory failure, stress ulcer, secondary epilepsy, urinary tract infection, sepsis, renal failure, acute coronary syndrome, venous thrombosis, and psychiatric symptoms, etc);		
	4) Proportion of patients with gastrointestinal haemorrhage within 7 days after EVT;		

Proportion of patients with pneumonia. 1) Inclusion Criteria Age 18 years; 2) The time from onset to randomization was within 12 hours; 3) Anterior circulation ischemic stroke was preliminarily determined according to clinical symptoms or imaging examination: 4) Occlusion of the intracranial internal carotid artery, the M1- or M2-segment of the middle cerebral artery confirmed by CT angiography (CTA), MR angiography (MRA), or digital subtraction angiography (DSA); Baseline National Institutes of Health Stroke Scale (NIHSS)>6; 5) 6) Baseline Alberta Stroke Program Early CT Score (ASPECTS)<6: Planned treatment with endovascular therapy (EVT); Informed consent obtained from patients or their legal representatives. Intracranial hemorrhage confirmed by cranial computed tomography (CT) or **Exclusion Criteria** magnetic resonance imaging (MRI). 2) mRS score ≥ 2 before onset. 3) Pregnant or lactating women. 4) Allergic to contrast agents or glucocorticoids. 5) Participating in other clinical trials. Systolic blood pressure >185 mmHg or diastolic pressure >110 mmHg, and oral antihypertensive drugs cannot control. Genetic or acquired bleeding constitution, lack of anticoagulant factors, or oral anticoagulants and INR > 1.7. 8) Blood sugar < 2.8 mmol/L (50 mg/dl) or > 22.2 mmol/L (400 mg/dl), platelet $< 90 \times 10^{9}/L$. The artery is tortuous so that the thrombectomy device cannot reach the target vessel. 10) Bleeding history (gastrointestinal and urinary tract bleeding) in recent 1 month 11) Chronic hemodialysis and severe renal insufficiency (glomerular filtration rate < 30 ml/min or serum creatinine > 220 umol/L [2.5 mg/ dL]). 12) Life expectancy due to any advanced disease < 6 months. Follow-up is not expected to be completed. 13) Intracranial aneurysm and arteriovenous malformation. 14) Brain tumors with imaging mass effect. 15) Systemic infectious disease. **Treatments** The emergency interventional team is on call 24 hours a day, 7 days a week. Each sub-center selects patients based on the above inclusion and exclusion criteria, and assigns them to either the intravenous methylprednisolone sodium succinate + endovascular treatment group (experimental group) or the placebo (i.e., intravenous methylprednisolone sodium succinate simulator) + endovascular treatment group (control group) in a 1:1 ratio by a web-based APP on mobile phone or computer. Randomization will be stratified by participating centres permutation block size of 8. After patients agree to participate and obtain a random number, they will receive intravenous methylprednisolone sodium succinate or placebo treatment as soon as possible, preferably before the establishment of arterial access and no later than 2 hours after the completion of endovascular treatment. Relevant time points (accurate to the minute) will be recorded truthfully and accurately. The effectiveness and safety of the two treatment regimens will be observed and evaluated.

Specific steps of treatment:

- 1) Apply for a randomization number and obtain the drug number, then quickly open the medicine box. The person opening the box signs the drug list, indicating the date and time of drug administration. Administer intravenous methylprednisolone sodium succinate or placebo, preferably before the establishment of arterial access and no later than 2 hours after the completion of endovascular treatment. The recommended specific dosage of intravenous methylprednisolone sodium succinate or placebo is 2 mg/kg (maximum dose of 160 mg) intravenously once daily, with the first dose administered before surgery for three consecutive days.
- 2) After patients agree to participate and obtain a random number, they will receive intravenous methylprednisolone sodium succinate or placebo as soon as possible, preferably before the establishment of arterial access and no later than 2 hours after the completion of endovascular treatment. Endovascular interventional treatment methods include mechanical thrombectomy, contact aspiration, intraarterial thrombolysis, balloon dilation, and/or emergency stent implantation.

Details of the above treatments must be recorded in detail in the CRF.

Sample Size Calculation and Statistical Methods

1. Sample size calculation

Based on the research results of published literature and combined with clinicians' experience, the 90-day mortality rates of the intravenous methylprednisolone sodium succinate + endovascular treatment group and the placebo + endovascular treatment group were estimated to be 29% and 38%, respectively. The sample size ratio between the two groups was 1:1. Assuming a two-sided α =0.05 and a power of 80%, the estimated sample size was 856 patients. Considering a 5% dropout rate, the maximum estimated sample size was calculated to be 902 patients using PASS 15.0, with 451 patients in each of the intravenous methylprednisolone sodium succinate + endovascular treatment group and the placebo + endovascular treatment group.

2. Statistical analysis

The intention-to-treat analysis was chosen for statistical analysis of trial efficacy, and the per-protocol dataset (i.e., statistical analysis based on data from all patients who met the trial protocol criteria) was used as a reference. The \times 2 test or Fisher's exact probability method was used to compare event rates, while the t-test or Mann-Whitney U test was used to compare continuous variables. Superiority evaluation indicators were adopted, and statistical tests were performed at a two-sided significance level of 0.05. Differences with $P \leq 0.05$ were considered statistically significant. All statistical analyses were performed using SAS.

3. Programming and analysis of the statistical analysis system.

Trial Schedule	Serial Number	Phases	Start Date	End Date
	1	Preparation	2024-02-01	2024-07-31
	2	Execution	2024-08-01	2025-07-31
	3	Follow-up and Data Collection	2025-08-01	2025-10-31
	4	Data Processing and Analysis	2025-11-01	2025-11-30
	5	Summarizion	2025-12-01	2025-12-31

Table of contents

Lis	t of A	bbreviations	1
Stu	dy Sy	ynopsis	2
1.	Stud	dy Background	3
2.	Stud	dy Objectives	7
3.	Stud	dy Design	7
	Sele 4.1. 4.2. 4.3. 4.4.	tction of Patients, Criteria for Termination and Privacy Protection. 11 Inclusion Criteria 12 Exclusion Criteria 12 Criteria for Termination 12 Privacy Protection 12	1 2 2
5.	Sam	pple Size Calculation	3
	6.1. 6.2.	Randomization	3
	7.1. 7.2. 7.3.	Implementation of Blinding14Emergency Unblinding Procedure14Unblinding Regulations14	4 4
8.	Tre	atment	4
	8.1. 8.2. 8.3. 8.4. 8.5. 8.6.	Treatment Groups	5 5 5 6
9.	Scho	edule of Assessments	6
	9.1. 9.2. 9.3.	Collection of Baseline Data18Randomized Group18Follow-up18	8
10.	End	lpoints of the Clinical Trial	7
	10. 10.	Primary Endpoints	9 9
	10	.2.1. Secondary Efficacy Endpoints	9

The First Affiliated Hospital of Fujian Medical University

11. Adverse Events	. 20
11.1. Definition	. 20
11.1.1. Definition of Adverse Events (AE)	20

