4.4. Privacy Protection

completely stored in the hospital where they receive treatment, and laboratory test reports and other examination results will be recorded in the patients' medical records. Only the investigators, ethics committees, and food and drug administration departments of this study will be allowed to access patients' medical records. Any public reports on the results of this study will not disclose the personal identities of patients. We will make every effort to protect the privacy of patients' personal medical information within the limits allowed by law.

According to medical research ethics, apart from personal privacy information, trial data will be available for public inquiry and sharing. Inquiry and sharing will be limited to web-based electronic databases to ensure that no personal privacy information is leaked.

5. Sample Size Calculation

Based on the research results from published literature and combined with clinicians' experience, the 90-day mortality rates for the intravenous methylprednisolone sodium succinate + endovascular treatment group (experimental group) and the placebo + endovascular treatment group (control group) are estimated to be 29% and 38%, respectively. Assuming a 1:1 ratio for the sample sizes of the two groups, a two-sided α of 0.05, and a power of 80%, the estimated sample size is 856 patients. Considering an expected dropout rate of 5%, the maximum estimated sample size, calculated using PASS 15.0, is 902 patients, with 451 patients in each of the intravenous methylprednisolone sodium succinate + endovascular treatment group (experimental group) and the placebo + endovascular treatment group (control group).

6. Randomization

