6.1. Randomized Grouping

Patients are randomly divided into two groups in a 1:1 ratio. This trial employs block randomization for group assignment, generating a random sequence in a 1:1 ratio. Investigators at each sub-center report to the lead investigator after patients sign the informed consent form, and the latter implements randomized group assignment through a centralized network APP.

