6.2. Concealing Group Allocation

- 1) This study employs a centralized randomization method. All odd and even random numbers in the random number sequence, generated by SAS software and corresponding to serial numbers (1, 2, 3...), are assigned to the experimental group and the control group, respectively, and recorded;
- A dedicated person is responsible for determining the grouping based on random numbers but does not participate in patient recruitment;
- The randomization schedule is sealed in opaque envelopes. The schedule is kept in triplicate, with one copy each retained by the principal investigator, the pharmacy, and the biostatistician. When unblinding or breaking the blind, the three copies of the randomization schedule must be opened simultaneously and in the presence of all parties. If one or more of the envelopes is damaged, it must be explained; otherwise, it will be announced that the grouping information has been leaked.

7. Blinding/Unblinding

This trial is blinded for investigators, patients, endpoint evaluators, and data analysts.

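### The synopsis, section 6.1 and section 6.2 describe the allocation method inconsistently, and the protocol prints a fixed block size and an odd/even arm rule that are small, avoidable risks to concealment and the blind

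*Combined protocol and SAP*

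**What the plan says.** Three places describe how the allocation list is built.

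- **Study Synopsis, Treatments:** "Randomization will be stratified by participating centres permutation block size of 8". No other place names a stratification factor or a block size.
- **Section 6.1:** "This trial employs block randomization for group assignment, generating a random sequence in a 1:1 ratio". It also says that the lead investigator carries out the assignment: "the latter implements randomized group assignment through a centralized network APP".
- **Section 6.2:** "All odd and even random numbers in the random number sequence, generated by SAS software and corresponding to serial numbers" 1, 2, 3 and so on "are assigned to the experimental group and the control group, respectively, and recorded". Neither block nor centre is mentioned.

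Other provisions bear on concealment. Section 7 states: "This trial is blinded for investigators, patients, endpoint evaluators, and data analysts". Section 7.1 makes active drug and placebo identical in appearance, but lists a random number among the items printed on the drug box. The synopsis has patients obtain a random number before they are dosed. Section 7.2 provides emergency envelopes, and section 7.3 voids the blind only when more than 20% are opened. Section 10.2.2 lists insulin use and new-onset diabetes among the glucocorticoid-related events.

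**The concern.** A programmer working from section 6.2 alone could build a different list from one working from the synopsis. The list used decides whether the arms are balanced within centre. That matters here because section 18.2 plans an analysis of each participating unit separately as well as combined, while the tests in section 12.3 are unadjusted. Readers also need to know whether centre was a stratification factor.

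Two disclosures add to this. A single block size is printed in a document that investigators hold. So is the rule that links the parity of a random number to the arm, while a random number is also handed to sites and shown on the box. Either could help someone at a site infer an assignment, although under different conditions.

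**Working it through.** **1. The plan's own figure.** Section 5 gives 29% v 38%, two-sided α 0.05, power 80% and 1:1 allocation. With the unpooled normal formula, n per arm = (1.960 + 0.842)² × (0.29×0.71 + 0.38×0.62) / 0.09² = 7.85 × 0.4415 / 0.0081 ≈ 428, so 856 in total. Dropout: 856/0.95 = 901.1, rounded up to 902 (451 per arm). Both figures reproduce, so the point concerns the list and not the sample size.

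**2. The three texts side by side.**

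| | Blocks | Block size | Centre strata | Odd/even rule |
|---|---|---|---|---|
| Synopsis | yes | 8 | yes | no |
| Section 6.1 | yes | not given | not given | no |
| Section 6.2 | not given | not given | not given | yes |

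Section 6.1 is a less detailed form of the synopsis. Section 6.2 is the outlier.

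**3. Balance if 6.2 is programmed with independent draws (an assumption).** The SD of the arm difference is √902 = 30.0, so the 95% range is about ±1.96 × 30.0 = ±59. The exact binomial 95% range for one arm is 422 to 480, and the chance of exactly 451:451 is 2.7%.

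The text available gives no centre sizes, so the centre sizes below are assumed:

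| Patients in centre | Chance that the arms differ by more than 4 |
|---|---|
| 8 | 7% |
| 16 | 21% |
| 24 | 31% |
| 40 | 43% |
| 80 | 58% |

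With blocks of 8 stratified by centre, the difference in a centre never exceeds 4, since each block holds four of each arm. In simulation, the SD of the overall difference is then about 5, 9 and 12 for an assumed 20, 50 and 100 centres.

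**4. Cost in power.** At 480:422 the variance of the risk difference rises by a factor of about 902²/(4 × 480 × 422) = 1.004. Power (pooled normal approximation, all 902 analysed) is 81.7%, against 81.8% at 451:451. With 856 analysed, the two ends of the 95% range (457:399 and 399:457) give 79.7% and 79.5%, against 79.8% at 428:428. The loss is 0.1 to 0.3 percentage point.

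**5. Predictability if the synopsis is programmed.** In a block of 2m, the expected number of assignments forced at the end is 2m/(m+1). For m = 4 this is 8/5 = 1.6 of 8, or 20%. Enumerating all 70 possible blocks, the best guess is right 66.6% of the time, against 50% by chance. Both figures require every earlier allocation in the block, and the block size, to be known. For known blocks of 4 and 6 the forced shares are higher (33% and 25%). Varied sizes therefore help only if they are kept from sites.

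**6. The label.** Section 6.2 ties odd to experimental and even to control. Sites obtain a random number, and section 7.1 prints one on the box. If these are the number used in 6.2, parity reveals the arm. If the printed number comes from a separate code list, it reveals nothing. The documents do not say which applies.

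**The case against.** The strongest reply is that the texts can be reconciled. Odd/even is only a mapping from number to arm. Applied to a random permutation of 1 to 8 within each block, it gives exactly 4:4; applied to a permutation of 1 to 902, it gives exactly 451:451. Section 6.1, directly before, says blocks. This stands. A reader might infer from 6.2 that the trial uses simple randomisation, but the documents do not show independent draws, and the SD of 30 holds only under that assumption. What remains is that 6.2 does not mention the blocks or centres on which the harmless reading depends.

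A reader might also infer that an equal split is promised and then lost. Section 5 gives a target, "with 451 patients in each of the intravenous methylprednisolone sodium succinate + endovascular treatment group" and likewise for placebo. Since 902/8 = 112.75, blocks of 8 would not guarantee it either.

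On predictability, the design answers most of the worry: allocation is central, investigators are blinded, active drug and placebo look alike, and the person who determines grouping does not recruit. Insulin use is a weak clue, because section 4.2 admits patients with glucose up to 22.2 mmol/L, so insulin can be expected in both arms. A reader might take the 20% as the share that sites can predict. The documents do not support that: with the blind intact, the practical gain from guessing is near zero. A fixed block in a double-blind trial is not in itself an error.

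**Conclusion.** The inconsistency is real and should be resolved, but its consequences are small and conditional. The balance and predictability points are alternatives: independent parity draws leave no block to predict, and centre-stratified blocks remove the imbalance.

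- **Section 6.2 with independent draws:** centre balance is not guaranteed, and the overall arm difference has an SD of about 30 of 902. The power cost is negligible.
- **Synopsis as written:** the disclosed fixed block is a small, avoidable risk. It matters only where earlier allocations become known, for example through opened emergency envelopes or visible glucocorticoid effects.
- **Parity rule:** this is the more direct reason for a change. If the number on the box is the number in 6.2, the protocol supplies the key to the blind. The documents leave this open, so it would be wrong to say that the blind is broken.

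Nothing here undermines the sample size or shows that a flawed list was used. It is a low-severity correction that is worth making because it needs no extra patients.

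**What to change.** 1. Delete the odd/even rule from section 6.2.
2. State one method, in the same words, in section 6.1 and the synopsis: central permuted blocks stratified by centre.
3. Use block sizes varied at random and record them only in a restricted randomisation file. Remove the block size from the synopsis.
4. Confirm in section 7.1 that the numbers given to sites and printed on drug boxes do not encode the arm.

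The wording costs almost nothing, and no patients or visits are added. The list must be regenerated. Because boxes are packed to the random codes and carry a random number, any already packed may need relabelling. This version is dated 23 July 2024 and execution is scheduled from 1 August 2024, so that is possible. If enrolment has started, document the list actually used and apply the change only to blocks not yet issued.

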19.1. Trial Principal Investigator	
19.2. Coordinating Committee	. 29

The First Affiliated Hospital of Fujian Medical University

19	9.3. Executive Committee	29
19	9.4. Data and Safety Monitoring Committee	29
19	9.5. Imaging Core Laboratory	29
20. I	Responsibilities of Each Party and Other Regulations	29
21. I	Declaration of Conflict of Interest	29
22. I	Protocol Signature Page	30
23. A	Appendix	31
I	Names, contacts, and contact information of each sub-center	31
II	Unblinding record form	35
24. I	References	36

Release date: July 23, 2024

1. Study Background

Acute stroke is a global disease that seriously threatens human life and health, and it is also one of the main causes of death in the global population.¹ Stroke has become the leading cause of death and disability among urban and rural residents in China, with about 2.4 million new stroke patients and about 1.1 million deaths each year, which brings a heavy burden to society and families. Stroke is divided into ischemic stroke and hemorrhagic stroke, and patients with ischemic stroke account for about 60% to 70% of the total. About 40% of acute ischemic strokes are caused by acute occlusion of large intracranial vessels.² Currently, early restoration of blood flow reperfusion and salvage of the ischemic penumbra are the theoretical cornerstones of ischemic stroke treatment.

Intravenous thrombolysis and intravenous thrombolysis combined with endovascular therapy have become standard treatment options for restoring blood flow in acute anterior circulation large vessel occlusive stroke, recommended by international guidelines IA.^{3,4} In recent years, with the advancement of endovascular therapy materials and the development of multimodal imaging assessment, four studies (RESCUE-Japan LIMIT⁵, ANGEL-ASPECT⁶、SELECT 2⁷、 TENSION⁸) have demonstrated the effectiveness and safety of endovascular therapy for patients with acute ischemic stroke caused by large infarct cores (ASPECTS score <6) due to anterior circulation large vessel occlusion. Currently, the recanalization rate of acute anterior circulation large vessel occlusive stroke through endovascular therapy has increased to 80.0%~94.0%, and restoring blood flow reperfusion is no longer a clinically difficult problem. However, a meta-analysis of previous clinical databases found that although blood flow recanalization plays an important role in acute anterior circulation large vessel occlusive stroke, the proportion of patients with good outcomes is less than 50.0%. Recently, the SELECT 2 study published in the New England Journal of Medicine reported that the mortality rate after endovascular therapy for patients with acute large infarct cores reached 38.2%. 8,9 Apparently, a treatment strategy that solely aims to improve the recanalization rate cannot fundamentally improve clinical benefits. Therefore, exploring ways to reduce patient mortality is expected to provide new insights for the treatment of acute anterior circulation large vessel occlusive stroke and help overcome the current research challenges in this field.

Intravascular therapy helps improve the prognosis of patients with acute ischemic stroke, but postoperative complications such as hemorrhagic transformation and malignant brain edema are important causes of death. Hemorrhagic transformation refers to the hemorrhage in the ischemic lesion caused by a variety of underlying mechanisms during ischemic stroke, among which the incidence of hemorrhagic transformation after intravascular treatment is about 46%-49.5%, and the incidence of symptomatic hemorrhagic transformation is 2%-16%. He is currently believed that oxidative stress, inflammatory response, and blood-brain barrier damage may be the underlying mechanisms of hemorrhagic transformation after intravascular treatment of acute ischemic stroke. Malignant cerebral edema is the main cause of early death and disability after ischemic stroke, with an incidence of 10%-78% in patients with ischemic stroke. It is characterized by a malignant course accompanied by severe cerebral edema, leading to cerebral hemia, death, or severe neurological dysfunction. The main mechanisms of cerebral edema after ischemic stroke include early cytotoxic edema and late vasogenic edema. Early cytotoxic edema is due to increased permeability of brain tissue and failure of Na+/K+ pump caused by ischemia and hypoxia, resulting in cell swelling, narrowing of extracellular space, and increased brain volume. Tissue necrosis and basement membrane degeneration cause damage to the blood-brain barrier, and 4-6 hours later, serum proteins begin to enter the brain from the blood,

inducing vasogenic edema and further increasing brain water content. In addition, reperfusion of the blood supply artery in the infarct area leads to more water passing through the damaged blood-brain barrier, combined with ischemia-reperfusion and hyperperfusion injury after mechanical thrombectomy, further exacerbating vasogenic edema, which peaks 1 to several days after ischemia and leads to malignant cerebral edema. Therefore, reducing complications such as hemorrhagic transformation and malignant cerebral edema after intravascular therapy is the key to ultimately reducing the mortality rate of patients with acute ischemic stroke.

Glucocorticoids are the most widely used and effective anti-inflammatory and immunosuppressive agents in clinical practice. They have the functions of stabilizing cell membranes, regulating the balance of water and electrolytes inside and outside cells, reducing the production of cerebrospinal fluid, and exerting non-specific antioxidant effects. They can also prevent cell membrane phospholipids from being damaged by free radicals, actively regulate and restore blood circulation in damaged brain tissue, and reduce cerebral edema.²¹ Methylprednisolone sodium succinate for injection is a medium-acting glucocorticoid that is widely used in clinical practice due to its small side effects and strong ability to penetrate the blood-brain barrier. Early basic research found that early combination therapy with methylprednisolone sodium succinate for injection can significantly increase cerebral blood flow reperfusion and reduce brain damage in a cat ischemia-reperfusion model.²² Recent studies have also shown that early combination therapy with methylprednisolone sodium succinate for injection can improve neurological deficits and increase the survival rate of newborn neurons by inhibiting neuronal apoptosis and down-regulating inflammatory responses in a rat ischemia-reperfusion model.^{23,24} A recent randomized controlled clinical trial (MARVEL) published in JAMA suggests that early combination therapy with methylprednisolone sodium succinate can reduce mortality and the incidence of symptomatic intracranial hemorrhage after intravascular therapy for patients with acute ischemic stroke. However, this study excluded patients with large infarct core strokes (ASPECTS score <6) who have more severe clinical symptoms and higher mortality and disability rates. 25 Currently, there is not enough evidence to support the safety and efficacy of early combination therapy with methylprednisolone sodium succinate for acute large core infarct reperfusion. To address this dilemma, there is an urgent need to conduct research specifically on this subset of patients.

Therefore, we intend to adopt a multi-center, prospective, randomized, double-blind controlled trial design to explore whether early combination therapy with methylprednisolone sodium succinate can improve the clinical prognosis of patients with acute large core infarcts based on revascularization.

2. Study Objectives

To explore the safety and efficacy of early combination therapy with methylprednisolone sodium succinate for injection after revascularization in patients with acute large core infarcts within 12 hours of onset.

3. Study Design

Using a multi-center, prospective, randomized, double-blind controlled trial design, we aim to investigate whether early combination therapy with methylprednisolone sodium succinate can improve the clinical prognosis of patients with acute large core infarcts based on revascularization.

According to the inclusion and exclusion criteria for clinical study subjects, eligible patients will be randomly assigned (1:1) to either the methylprednisolone sodium succinate for injection + intravascular treatment group

(experimental group) or the placebo (methylprednisolone sodium succinate simulator) + intravascular treatment group (control group). Physicians who are unaware of the clinical data information will follow up and evaluate patients' 90-day modified Rankin Scale (mRS) scores through outpatient visits or phone calls, and conduct safety assessments simultaneously. ²⁶ The specific trial process, trial steps, and items to be evaluated at each time point are shown in Figure 1 and Table 1, respectively.

[figure not shown]

Figure 1 Flow Chart

Release date: July 23, 2024

4. Selection of Patients, Criteria for Termination and Privacy Protection

